10.8. Overdose

PEGPH20 and pembrolizumab will be administered by IV infusion at a qualified and experienced clinical study site. The potential for drug overdose is therefore minimal. However, should an overdose occur, the infusion should be stopped immediately. A blood PK plasma sample should be taken as soon as possible, with a notation of the time of sampling relative to the time of cessation of the infusion. The Investigator should also monitor the subject with appropriate blood counts and blood chemistry tests, and should also provide supportive therapy, as necessary. Contact the Halozyme Medical Monitor, or designee, WITHIN 24 HOURS.

There are no data regarding PEGPH20 overdose in humans. However, the likelihood of significant MSEs (such as pain, spasms, and weakness) increases with increasing PEGPH20 dose. An overdose and AEs should be treated as per standard medical practice. There is no known antidote for PEGPH20.

Overdose of pembrolizumab should be managed per the Prescribing Information.

Dosing details should be captured in the eCRF. If the subject receives a dose of a study drug that exceeds protocol specifications and the subject is symptomatic, then the symptom(s) should be documented as AEs in the eCRF and, if serious, submitted to the Sponsor's designated safety contact on an SAE Report Form. Do not record the overdose as an AE if the subject is not symptomatic.

10.9. Data Monitoring Committee

An independent DMC will review all available safety data from the first 3 NSCLC subjects and first 3 gastric adenocarcinoma subjects who have completed Cycle 1 in Dose Expansion to determine if the safety and tolerability profile of the PEGPEM combination is acceptable (refer to the DMC charter for additional details). The DMC will also continue to periodically review safety data to protect subject welfare and identify potential safety signals.

10.10. Unblinding

No part of the study is blinded.

10.11. Reporting Safety Information to the Regulatory Authorities and to the Institutional Review Board

The Sponsor will determine if SAEs are suspected unexpected serious adverse reactions (SUSARs), and if so will expedite reporting to Regulatory Authorities according to applicable Clinical Trials Regulations.

The Sponsor and/or a designated agent may provide written safety reports or other safety-related communications to the Investigator. The Investigator will ensure that these reports are reviewed and processed in accordance with regulatory and IRB/EC requirements and archived in the site's study file.

At the completion or early termination of the study, the Investigator will submit a final report to the IRB/EC within the applicable time frame.

10.12. Concomitant Medications

Any medication received during the study, other than a designated study drug (PEGPH20 or pembrolizumab), is regarded as concomitant medication. Record concomitant medications taken after the subject signs the ICF during the Screening period (≤28 days prior to Study Day 1) through 30 days after the End of Treatment Visit on the Concomitant Medications eCRF.

Update information on concomitant medications, including medication used to treat an AE, at each visit according to the study schedule of events. At each visit, ask subjects if there have been any changes in their prescription or non-prescription medications since their last visit.

Subjects may receive medications during the study including, but not limited to, antibiotics, analgesics, antipyretics, etc., when clinically indicated. Prohibited medications are identified in Section 8.4.

Piroxicam and toradol used to decrease the severity of musculoskeletal symptoms should be documented and recorded in the eCRF. Prescribed medication such as narcotics, muscle relaxants and other analgesics (with the exceptions of steroids), OTC drugs and physical therapy can also be used at the Investigator's discretion and should be documented and recorded in the eCRF. Dexamethasone may be used at the Investigator's discretion and following a discussion with the Sponsor, and should be documented and recorded in the eCRF. For additional details, refer to Table 6.

Enoxaparin and any other anticoagulants should also be documented and recorded in the eCRF.

10.12.1. Piroxicam and Toradol

Refer to the current piroxicam and toradol Prescribing Information for prescribing information and toxicity profile.

Piroxicam and toradol have been investigated in an animal model of MS events and may be helpful in decreasing the severity of MSEs in subjects. Piroxicam (20 mg) will be administered at least 1-2 hours prior to PEGPH20 administration on the day of dosing (timing will be at the Investigator's discretion based on the piroxicam manufacturer's Prescribing Information and subject's convenience) to minimize the severity of MSEs. The prophylactic use of a proton pump inhibitor is mandated for all subjects while receiving the study drug (e.g. 20 mg omeprazole daily or OTC equivalent).

Toradol should not be administered concurrently with piroxicam as it is contraindicated in the Toradol Prescribing Information to administer toradol simultaneously with other NSAIDs because of the cumulative risk of inducing serious NSAID-related side effects. If piroxicam is used chronically, consideration should be given to begin an H2 blocker to decrease the risk of gastric irritation.

If side effects are observed following administration of NSAIDs, the dosing of piroxicam may be adjusted at the Investigator's discretion upon discussion with the Sponsor.

10.12.2. Enoxaparin

Refer to the current enoxaparin Prescribing Information for prescribing information and toxicity profile.

All gastric adenocarcinoma subjects with or without a history of DVT will be given enoxaparin 40 mg/day (pre-filled syringes of enoxaparin are allowed), for prophylaxis of TE events, given the high incidence seen in this tumor type. PEGPH20 will be discontinued for subjects who experience any TE requiring full-dose anticoagulation while on study. Treatment with pembrolizumab, however, may continue as deemed appropriate by the Investigator.

If in gastric adenocarcinoma subjects, enoxaparin is discontinued for any reason, PEGPH20 will also be discontinued. Treatment with pembrolizumab, however, may continue as deemed appropriate by the Investigator.

10.12.3. Aspirin

All NSCLC subjects will be given enteric-coated 81 mg of aspirin/day for prophylaxis of TE events, given the high incidence seen in this tumor type.

10.12.4. Dexamethasone

As this study uses an immunotherapeutic agent and dexamethasone may suppress an immune response, it should only be used when prescribed by the Investigator and following a discussion with the Sponsor. Dexamethasone may be used to attenuate musculoskeletal symptoms that may occur in subjects treated with PEGPH20 and/or pembrolizumab if prescribed by the Investigator (and following a discussion with the Sponsor). In this situation dexamethasone may be given orally, intramuscularly, or intravenously.

Refer to a current dexamethasone Prescribing Information for prescribing information and toxicity profile.

11. STATISTICS

11.1. Statistical Methods

In general, continuous variables will be summarized using descriptive statistics (N, mean, standard deviation, median, minimum, and maximum). Categorical variables will be presented using frequencies and percentages. Dose escalation data summaries will be presented by PEGPH20 dose level. All statistical analyses and data listings will be performed using SAS version 9.3 or higher (Cary, NC).

11.1.1. Randomization and Blinding

This is a multicenter, open-label, non-randomized study.

11.1.2. Sample Size

In the dose escalating portion, there may be up to 5 dose levels for a total of approximately 30 subjects.

In the Dose Expansion portion, approximately 51 subjects with HA-high tumors will be enrolled (30 with HA-high tumors in NSCLC cohort and 21 with HA-high tumors in the gastric adenocarcinoma cohort).

KEYNOTE-001 study data presented at the American Society of Clinical Oncology 2016 (Hui 2016) showed that when treated with pembrolizumab alone, treatment naïve subjects who had evaluable PD-L1 Tumor Proportion Score [TPS] levels had an ORR of 29% and previously treated subjects who had evaluable PD-L1 TPS levels had an ORR of 21%. Under the assumption that no more than 40% of the subjects enrolled in this study will be treatment naïve, ORR in the combined NSCLC population is expected to be approximately 24% when treated with pembrolizumab alone. A 20% improvement in ORR is considered clinically meaningful when PEGPH20 is added to pembrolizumab. Under these conditions, 30 NSCLC subjects would provide approximately 80% power at the hypothesized ORR of 44% when the null hypothesis H0: ORR ≤24% is tested against H1: ORR >24% using an exact one-sided binomial test at a 10% significance level.

KEYNOTE-012 study data showed that the ORR in PD-L1 positive gastric cancer subjects is about 22% (Muro 2016). Since subjects will not be selected based on PD-L1 expression levels prospectively in this study, in order to accommodate all subjects (irrespective of PD-L1 expression levels), a conservative ORR of 15% is assumed with pembrolizumab treatment alone and it is further assumed that the addition of PEGPH20 to pembrolizumab will lead to a clinically meaningful improvement of 20% in ORR to 35%. Under these assumptions, 21 subjects will provide approximately 80% power at the hypothesized ORR of 35% when the null hypothesis H0: ORR ≤15% tested against H1: ORR >15% using an exact one sided binomial test at a 10% significance level.

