5.1.2. Dose Expansion

Note: The objectives described below will be evaluated in HA-high subjects with relapsed/refractory NSCLC and HA-high subjects with relapsed/refractory gastric adenocarcinoma.

Primary Objective

• To evaluate the efficacy of PEGPEM as assessed by ORR based on RECIST v1.1

Secondary Objectives

- To evaluate the efficacy of PEGPEM as assessed by DOR, DCR and PFS based on RECIST v1.1, and OS
- To evaluate the efficacy of PEGPEM as assessed by ORR, DOR, DCR and PFS based on immune-response related criteria (irRC)

- To characterize the PK of PEGPH20 when given in combination with pembrolizumab
- To evaluate the safety and tolerability profile of PEGPEM

Exploratory Objectives

- To evaluate the efficacy of PEGPEM, as assessed by ORR, DOR, DCR, and PFS based on RECIST v1.1 criteria and irRC, by PD-L1 expression levels
- To assess the treatment effect of PEGPEM as follows:
 - Based on HA levels in plasma and tumors, or other potential biomarkers.
 - Based on tumor blood flow and metabolic activity as assessed by dynamic contrast-enhanced magnetic resonance imaging (DCE-MRI) and positron emission tomography (PET)/computed tomography (CT) scans, respectively.
- To assess the PK of pembrolizumab when given in combination with PEGPH20

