6.1.2. Phase 1b Dose Expansion

Approximately 51 HA-high subjects will be studied in the Dose Expansion portion at the RP2D identified in the Dose Escalation portion:

- Approximately 30 subjects with Stage IIIB or IV NSCLC, previously untreated or treated and having failed no more than 1 previous platinum-based chemotherapy (refer to Inclusion Criterion #3)
- Approximately 21 subjects with relapsed/refractory gastric adenocarcinoma having failed no more than 2 previous chemotherapy regimens.

The study medication dosing and treatment schedule are shown in Table 5.

Table 5: Study Medication Dosing and Treatment Schedule - Dose Escalation and Dose Expansion

Time point	PEGPEM Treatment	
Subjects with NSCLC or Gastric Adenocarcinoma		
Cycle 1 and Beyond (Each Cycle 21 Days)		
Week 1		
Day 1	PEGPH20	
	Pembrolizumab (4-6 hours after PEGPH20)	
Week 2		
Day 8	PEGPH20	
Week 3		
Day 15	PEGPH20	

Abbreviations: PEGPEM = PEGPH20 in combination with pembrolizumab; PEGPH20 = PEGylated Recombinant Human Hyaluronidase; NSCLC = non-small cell lung cancer.

Notes: Dose interruption and modifications are permitted; refer to Section 8.3 for further guidance. Visit window is ± 2 days of the specified times.

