- 3. Dose Expansion portion NSCLC subjects: Histologically confirmed and documented, previously untreated or treated stage IIIB or IV NSCLC. Previously treated subjects must have failed no more than 1 previous platinum-based chemotherapy regimen for locally advanced or metastatic disease. Previously treated subjects with NSCLC who are known to be EGFR-mutation positive must have received an EGFR inhibitor and subjects who are known to be ALK-mutation positive must have received an ALK inhibitor (subject's documented EGFR/ALK mutation status and/or confirmation reports/molecular pathology/analysis reports should be included in the subject's medical records and made available for Sponsor/Sponsor representative[s] review). Gastric adenocarcinoma subjects: histologically confirmed and documented previously treated relapsed/refractory locally advanced or metastatic gastric adenocarcinoma having failed no more than 2 previous chemotherapy regimens for locally advanced or metastatic disease.
 - a. Subjects with GEJ tumors are eligible.
 - b. For subjects with either NSCLC or gastric cancer, prior treatment administered in the adjuvant setting is permitted provided it was administered at least 6 months prior to first-line therapy for metastatic disease.
 - c. For previously treated subjects with NSCLC, prior treatment with or without bevacizumab (AVASTIN®) or bevacizumab biosimilars is allowed.
 - d. For previously treated subjects with NSCLC, prior maintenance treatment with bevacizumab, pemetrexed (ALIMTA®), or erlotinib (TARCEVA®) is allowed.
 - e. For subjects with HER2+ gastric cancer, prior treatment with trastuzumab (HERCEPTIN®) is required (subject's documented HER2 status and/or confirmation reports/molecular pathology/analysis reports should be included in the subject's medical records and made available for Sponsor/Sponsor representative[s] review).

- 4. Prior to enrollment, confirmation of the following must be obtained:
 - a. **Dose Escalation portion** Available tumor tissue in a formalin-fixed paraffin-embedded (FFPE) block or 5-10 unstained consecutive core biopsy slides from 1 tumor tissue block that meet specific tissue sample requirements are preferred but not mandatory for enrollment in this portion of the study. **Note:** Fine needle aspirates or brushing biopsies will not be acceptable.

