## 2.2 Dose Expansion

The objectives described below will be evaluated in hyaluronan-high (HA-high) subjects with relapsed/refractory NSCLC and HA-high subjects with relapsed/refractory gastric adenocarcinoma.

Statistical Analysis Plan Version Number: 1.0

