#### 4.8 Subgroup Analysis

No subgroup analyses are planned.

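### The NSCLC response-rate null assumes at most 40% untreated subjects, but nothing limits or examines that share; the false-positive rate would pass 10% only if about half or more were untreated

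*Protocol*

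**What the plan says.** Protocol 11.1.2 and SAP 4.12 take two response rates for pembrolizumab alone from a cited study: 29% in treatment-naive and 21% in previously treated NSCLC. They combine these into an expected rate of about 24%, on the assumption that "no more than 40% of the subjects enrolled in this study will be treatment" naive. The sizing statement is that "30 NSCLC subjects would provide approximately 80% power at the hypothesized ORR of 44" percent, "using an exact one-sided binomial test at a 10% significance level". The null actually tested is 23% (protocol 11.1.6.1, SAP 4.7.2).

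Eligibility is open on line of therapy. Inclusion criterion 3 (protocol 7.1) admits "previously untreated or treated stage IIIB or IV NSCLC", and protocol 6.1.2 plans for "Approximately 30 subjects with Stage IIIB or IV NSCLC, previously untreated or treated", with no split. The registration text (protocol 8.1.1.1 and 8.6) mentions no cap or stratum.

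The objectives describe a narrower population. The note in protocol 5.1.2, also in the synopsis, names "relapsed/refractory NSCLC and HA-high subjects with relapsed/refractory gastric adenocarcinoma". SAP 2.2 says the objectives "will be evaluated in hyaluronan-high (HA-high) subjects with relapsed/refractory NSCLC".

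On analysis, SAP 4.7.5 marks covariate adjustment as not applicable and SAP 4.8 states "No subgroup analyses are planned". The number of prior therapy lines is summarised as a baseline characteristic (SAP 4.6.2), and efficacy endpoints are listed by subject (SAP 4.7).

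**The concern.** A single-arm test is only as good as its benchmark. Here the benchmark is a weighted average whose weights depend on who is enrolled, and the condition behind the weights is written down but neither enforced nor checked. If untreated subjects are well represented, pembrolizumab alone is expected to exceed the null, and a significant result could partly reflect line of therapy rather than PEGPH20. If few are untreated, the test is harder to pass than it appears.

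The objectives add a second problem. Untreated subjects fall outside the stated target population but inside the primary test, so it is unclear whether the pooled result answers the stated question.

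**Working it through.** **Inputs.** Rates of 29% and 21%, the 40% ceiling, n = 30, one-sided exact 10% test, alternative 44% (protocol 11.1.2); tested null 23% (protocol 11.1.6.1, SAP 4.7.2); 17 NSCLC subjects enrolled in Dose Expansion (SAP 4.7.2).

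**The plan's own figures.** At untreated share f, the expected rate is 0.21 + 0.08f.
- f = 0.40 gives 0.242, which reproduces the 24%.
- The tested 23% corresponds to f = (0.23 − 0.21)/0.08 = 0.25.
- At n = 30, P(X ≥ 10) is 0.162 under 24% and 0.131 under 23%. P(X ≥ 11) is 0.083 and 0.064. The test therefore rejects at 11 or more responders under either null.
- Power at 44% is P(X ≥ 11) = 0.840, somewhat above the stated 80% or so. That difference does not affect this point.

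**False-positive rate by mix.** With u untreated of n and no PEGPH20 effect, responders are Bin(u, 0.29) + Bin(n − u, 0.21). The false-positive rate is the probability that this sum reaches the cutoff.

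| n = 30, cutoff 11: untreated | Rate | n = 17, cutoff 7: untreated | Rate |
|---|---|---|---|
| 0 | 0.036 | 0 | 0.048 |
| 12 | 0.087 | 7 | 0.093 |
| 14 | 0.098 | 8 | 0.102 |
| 15 | 0.105 | 12 | 0.140 |
| 18 | 0.125 | 14 | 0.162 |
| 30 | 0.230 | 17 | 0.198 |

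At n = 17 the cutoff of 7 also applies under both 23% and 24%.

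**Evaluable number.** SAP 4.4.6 and 4.7 analyse ORR in the Tumor Response Evaluable Population, which may be smaller than 17. The threshold moves irregularly because the test is discrete:

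| Evaluable n | Cutoff | Untreated number at which 10% is passed | Rate if all untreated |
|---|---|---|---|
| 17 | 7 | 8 | 0.198 |
| 16 | 7 | 11 | 0.153 |
| 15 | 7 | 14 | 0.113 |
| 14 | 6 | 6 | 0.195 |

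**Effect of a mix-weighted null at n = 17.** With p0 = (0.29u + 0.21(17 − u))/17, the exact cutoff stays at 7 for u = 0 to 7 and becomes 8 for u = 8 to 17. The false-positive rate is then below 0.10 at every mix. Power at a true ORR of 44% is 0.680 with cutoff 7 and 0.492 with cutoff 8.

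**The case against.** The strongest reply is that the harm is conditional and the slack is real. The exact test is discrete, so passing 40% untreated does not by itself break the 10% level: at n = 30 it takes 15 untreated. The largest rates need nearly everyone to be untreated, and nothing in the documents suggests that mix. This stands. A reader might infer that any share above 40% inflates the error, or that inflation occurred in this trial; the documents support neither.

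A reader might also infer that response by line of therapy cannot be recovered. That goes too far. Prior lines are summarised and listed at baseline (SAP 4.6.2), and efficacy endpoints are listed by subject. What is missing is a planned summary and a planned check of the assumption.

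It is also fair that this is an open-label Phase 1b study, that enrolment stopped on 31 May 2018, and that SAP 4.7.2 already attaches a caveat to the NSCLC result. That caveat concerns low power, however, not whether the benchmark suits the subjects enrolled.

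Finally, replacing a prespecified null after enrolment has closed in an open-label study is hard to defend. That stands, and it is why the mix-weighted test belongs beside the prespecified one rather than in its place.

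The mismatch in the objectives is a wording matter: the design and eligibility text plainly include untreated NSCLC. It does not change any error rate.

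**Conclusion.** The point holds in a bounded form. The NSCLC null depends on an untreated share that the plan neither limits nor examines. With 30 subjects the false-positive rate runs from 3.6% (none untreated) through 8.7% (12 untreated) to 23.0% (all untreated), passing 10% from 15. With 17 evaluable subjects it passes 10% from 8 untreated and reaches 19.8%; a smaller evaluable number shifts the threshold.

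These figures take 29% and 21% as the true rates for pembrolizumab alone in HA-high subjects, although the documents cite them for subjects with evaluable PD-L1 scores. They also assume independent responses. The untreated share among those enrolled is not reported, so the documents do not show that the level was exceeded. What can be said is that the NSCLC result cannot be properly interpreted until that share is shown.

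**What to change.** Keep the prespecified 23% test as primary. In SAP 4.7.2 add, for NSCLC Dose Expansion in the Tumor Response Evaluable Population:

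- (a) the observed numbers of untreated and previously treated subjects;
- (b) confirmed ORR with an exact 80% confidence interval separately for each group;
- (c) a sensitivity exact test at the one-sided 10% level against p0 = (29% × untreated + 21% × previously treated)/n, with a statement that any claim of a PEGPEM effect in NSCLC will be qualified if the two tests disagree.

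Amend SAP 4.8 so that it does not contradict (b). Correct the population note in the synopsis, protocol 5.1.2 and SAP 2.2 to include previously untreated NSCLC.

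The cost is one table from data already collected. Intervals by line will be wide. The sensitivity benchmark is stricter when about half or more are untreated: at n = 17 its cutoff moves from 7 to 8, and power at 44% falls from 68% to 49%. An enrolment cap on untreated subjects would have enforced the assumption but is moot now that enrolment has stopped.

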4.6.2. Pembrolizumab for Treatment of Gastric Adenocarcinoma

Treatment choices for gastric cancer depend on tumor type and stage. The only hope for cure currently rests on removal of the malignant tissue either endoscopically or by surgical resection. For advanced disease, treatment is largely palliative and consists of a combination of surgery, chemotherapy, and radiation. Overall, the results of current therapy for advanced disease are poor with low 5 years survivals. Immunotherapy provides another dimension to the prevention and management of gastric cancer and offers hope of breaking through current constraints (Matsueda 2014).

The safety and efficacy of pembrolizumab was assessed in a phase 1b study in patients with advanced gastric cancer in KEYNOTE-012 (Clinicaltrials.gov identifier NCT01848834). Using a prototype immunohistochemistry assay, PD-L1 expression was assessed in archival tumor samples from patients with recurrent/metastatic adenocarcinoma of the stomach or gastroesophageal junction. Eligible patients with PD-L1 staining in stroma or ≥1% of tumor cells were enrolled and treated with pembrolizumab 10mg/kg every 2 weeks for up to 24 months or until complete response (CR), disease progression or unacceptable toxicity. AEs were monitored and graded per the National Cancer Institute Common Terminology Criteria for Adverse Events (NCI CTCAE c4.0). Radiographic imaging was performed every 8 weeks. Primary efficacy endpoint was ORR assessed by Response Evaluation Criteria in Solid Tumors (RECIST) v1.1.

Of the 162 patients screened, 65 (40%) were PD-L1 positive. Of these 65 patients, 39 enrolled. The number of prior therapies for advanced disease ranged from 0 to 5; 67% received ≥2 prior therapies. Median follow-up duration was 8.8 months (range 6.2-12.6); 13 patients (33%) remain

on therapy. Four patients experienced 5 total grade 3-5 drug-related adverse events: peripheral sensory neuropathy, fatigue, decreased appetite, hypoxia, and pneumonitis (n = 1 each). There was 1 drug-related death (hypoxia). ORR was 22% (95% CI 10-39) by central review and 33% (95% CI 19-50) by Investigator review. Median time to response was 8 weeks (range 7-16), with a median response duration of 24 weeks (range 8+ to 33+). PD-L1 expression level was associated with ORR (1-sided P = 0.10). The 6-month PFS rate was 24%. The 6-month OS rate was 69%.

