#### 4.6.2 Baseline Disease Characteristics

A descriptive summary of baseline disease characteristics of the subjects in the Safety Population and Efficacy Population by cancer type and in total will be produced for the following: initial disease stage, time from initial diagnosis to enrollment, current disease stage (months), time from current diagnosis to enrollment (months), significant past medical history or ongoing (yes, no), tobacco usage status (current, former, or never), alcohol usage status (current, former, or never), number of cancer therapy lines, prior cancer therapies/medications (yes, no), prior cancer resections (yes, no), prior cancer radiation (yes, no), PD-L1 expression level in tumor tissues on tumor cells assessed by NeoGenomics for subjects with gastric adenocarcinoma cancer type and Ventana for subjects with NSCLC cancer type at Baseline along with positive and negative status, and ECOG performance status at Screening and on study day 1.

The positive and negative status for PD-L1 on tumor cells at Baseline are determined based on the following (see prescribing information of Keytruda®):

- Subjects with gastric adenocarcinoma cancer type: the PD-L1 status is provided by NeoGenomics based on Combined Positive Score (CPS) where PD-L1 status is assigned as negative if CPS = 0 and positive if CPS ≥ 1.
- Subjects with NSCLC cancer type: the PD-L1 status will be derived based on Tumor Proportion Score (TPS) from Ventana data as follows:
  - If pembrolizumab is the first-line treatment, the PD-L1 status will be considered as negative if TPS < 50 and positive if TPS  $\ge$  50.
  - If pembrolizumab is the second-line treatment or beyond, the PD-L1 status will be considered as negative if TPS = 0 and positive if  $TPS \ge 1$ .

A listing of baseline disease characteristics will also be provided.

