#### 4.7.2 Analysis of Unconfirmed/Confirmed ORR, DCR and DOR

The primary efficacy endpoint of the study in Dose Expansion portion is PEGPEM treatment effect on confirmed ORR based on tumor assessments from the Investigator using RECIST v1.1. The statistical hypothesis tests for the primary endpoint are as follows:

- NSCLC cancer type:  $H_0$ : ORR  $\leq 23\%$ ;  $H_1$ : ORR > 23%
- Gastric adenocarcinoma cancer type:  $H_0$ : ORR  $\leq 15\%$ ;  $H_1$ : ORR > 15%

The hypothesis tests will be conducted using the one-sided exact binomial test at the significance level of 0.1. Thus, confirmed ORR and its two-sided 80% exact confidence interval will be provided to test each of the hypotheses above. If the lower limit of the exact confidence interval lies above 23% or 15% for NSCLC or gastric adenocarcinoma cancer types respectively, the respective null hypothesis will be rejected concluding a statistically significant effect of PEGPEM treatment in the respective cancer type. In addition, best overall response data will be summarized in frequency and percentage format by cancer type and the two-sided, exact 80% confidence intervals for the unconfirmed ORR and DCR will also be provided. Further, median DOR and its 80% confidence interval will be calculated and reported. Unconfirmed/confirmed ORR, DCR, and DOR will also be calculated based on irRC and displayed in summary tables and listings.

Additional efficacy analyses of ORR, DCR, and DOR related to NSCLC cancer type will also be performed using RECIST v1.1 data from Imaging Endpoints.

Note: Halozyme made the decision to discontinue further enrollment into the study on 31 May 2018. At the time of the early termination, a total of 25 gastric adenocarcinoma cancer subjects and 17 NSCLC subjects have been enrolled in the Dose Expansion portion. The planned sample size in the Dose Expansion portion is approximately 51 subjects (approximately 30 with HA-high tumors in NSCLC and approximately 21 with HA-high tumors in the gastric adenocarcinoma cohort). Therefore, a caveat regarding the interpretation of the results will be provided for the NSCLC cohort which is underpowered because of the early termination.

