## 4.12 Sample Size Determination

In the Dose Escalating portion, there may be up to 5 dose levels for a total of approximately 30 subjects.

In the Dose Expansion portion, approximately 51 subjects with HA-high tumors will be enrolled (30 with HA-high tumors in NSCLC cohort and 21 with HA-high tumors in the gastric adenocarcinoma cohort).

KEYNOTE-001 study data presented at the American Society of Clinical Oncology 2016 (Hui 2016) showed that when treated with pembrolizumab alone, treatment naïve subjects who had evaluable PD-L1 Tumor Proportion Score (TPS) levels had an ORR of 29% and previously treated subjects who had evaluable PD-L1 TPS levels had an ORR of 21%. Under the assumption that no more than 40% of the subjects enrolled in this study will be treatment naïve, ORR in the combined NSCLC population is expected to be approximately 24% when treated with pembrolizumab alone. A 20% improvement in ORR is considered clinically meaningful when PEGPH20 is added to pembrolizumab. Under these conditions, 30 NSCLC subjects would provide approximately 80% power at the hypothesized ORR of 44% when the null hypothesis H0: ORR  $\leq$ 24% is tested against H1: ORR  $\geq$ 24% using an exact one-sided binomial test at a 10% significance level. KEYNOTE-012 study data showed that the ORR in PD-L1 positive gastric cancer subjects is about 22% (Muro 2016). Since subjects will not be selected based on PD-L1 expression levels prospectively in this study, in order to accommodate all subjects (irrespective

Statistical Analysis Plan Version Number: 1.0

of PD-L1 expression levels), a conservative ORR of 15% is assumed with pembrolizumab treatment alone and it is further assumed that the addition of PEGPH20 to pembrolizumab will lead to a clinically meaningful improvement of 20% in ORR to 35%. Under these assumptions, 21 subjects will provide approximately 80% power at the hypothesized ORR of 35% when the null hypothesis H0: ORR  $\leq$ 15% tested against H1: ORR >15% using an exact one sided binomial test at a 10% significance level.

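### The 15% gastric null keeps the one-sided 10% error only up to a certain PD-L1-positive share; enrolment does not control that share, and the SAP has no way to read a PD-L1-rich positive result

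*Protocol*

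**What the plan says.** Protocol 11.1.2 starts from about 22% ORR in PD-L1-positive gastric subjects on pembrolizumab. Because this trial does not select on PD-L1, it moves to a lower figure: "a conservative ORR of 15% is assumed with pembrolizumab treatment alone". SAP 4.12 repeats this. Neither document gives the PD-L1 mix behind the 15%, or an ORR for PD-L1-negative subjects. The design is 21 subjects, 15% against 35%, with an exact one-sided binomial test at 10% and about 80% power.

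Protocol 4.6.2 gives the only PD-L1 prevalence for gastric cancer: "Of the 162 patients screened, 65 (40%) were PD-L1 positive". That source used a prototype assay, counting staining in stroma or in at least 1% of tumor cells. SAP 4.6.2 classifies this trial's gastric subjects differently: "PD-L1 status is assigned as negative if CPS = 0 and positive if CPS ≥ 1".

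Inclusion criteria 3, 4 and 13 require HA-high tumors and tissue for PD-L1 testing, but set no PD-L1 cap, quota or stratum. Protocol 8.2.17.1.4 makes the gastric PD-L1 testing retrospective.

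Under SAP 4.7.2, if the lower limit of the exact 80% interval is above 15%, "the respective null hypothesis will be rejected concluding a statistically significant effect of PEGPEM treatment in the respective cancer type". The same section records 25 gastric subjects enrolled in Dose Expansion.

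Protocol 11.1.7.3 plans descriptive ORR by PD-L1 level. SAP 4.3.2 still lists that endpoint, but SAP 4.7.4 limits PD-L1 to listings, SAP 4.8 plans no subgroup analyses, and SAP section 5 does not record the change.

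**The concern.** There is no control arm, so the attribution to PEGPH20 rests on 15% being a fair value for pembrolizumab alone in the subjects actually enrolled. By the plan's own reasoning that value depends on PD-L1: it was lowered from 22% because the cohort would include PD-L1-negative subjects. If the enrolled cohort is mostly PD-L1-positive, its pembrolizumab-alone ORR lies above 15% and the fixed test rejects more often than 10% with nothing contributed by PEGPH20. The share will be known by the time of analysis, because expansion tissue is mandatory and baseline status is tabulated, yet the SAP makes no use of it when interpreting the primary result.

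**Working it through.** **Inputs.** Null 15%, alternative 35%, N = 21, one-sided alpha 0.10 (protocol 11.1.2); 25 enrolled (SAP 4.7.2); 22% ORR in PD-L1-positives (protocol 11.1.2 and 4.6.2); 65/162 = 40% positive (protocol 4.6.2). The ORR in PD-L1-negatives, q, is not in the documents. I assume 0%, 5% and 10%.

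**Step 1, the plan's own figure.** With X binomial:
- N = 21: reject at 6 or more. P(X ≥ 6 | 0.15) = 8.3%; P(X ≥ 6 | 0.35) = 79.9%. The stated 80% is reproduced. The SAP's interval rule agrees: the exact 80% lower limit is 15.8% at 6/21 and 12.1% at 5/21.
- N = 25: reject at 7 or more. Size 7.0%, power 82.7%.

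**Step 2, how far the true pembrolizumab-alone ORR can rise before 10% is exceeded.** Solving P(X ≥ 6 | 21, p) = 0.10 gives p = 15.8% (15.75%). Solving P(X ≥ 7 | 25, p) = 0.10 gives p = 16.3% (16.32%).

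**Step 3, convert to a PD-L1-positive share f.** The cohort's pembrolizumab-alone ORR is 0.22f + q(1 − f), so the largest tolerable share is f = (p − q)/(0.22 − q).

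| q | N = 21 | N = 25 |
|---|---|---|
| 0% | 0.1575/0.22 = 72% | 0.1632/0.22 = 74% |
| 5% | 0.1075/0.17 = 63% | 0.1132/0.17 = 67% |
| 10% | 0.0575/0.12 = 48% | 0.0632/0.12 = 53% |

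**Step 4, chance of rejecting 15% with no PEGPH20 effect.** The three values in each cell are for q = 0%, 5% and 10%.

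| Share positive | Pembrolizumab-alone ORR | N = 21 (reject at 6) | N = 25 (reject at 7) |
|---|---|---|---|
| 40% | 8.8%, 11.8%, 14.8% | 0.8%, 3.0%, 7.8% | 0.5%, 2.2%, 6.5% |
| 60% | 13.2%, 15.2%, 17.2% | 4.9%, 8.7%, 13.8% | 3.9%, 7.4%, 12.4% |
| 80% | 17.6%, 18.6%, 19.6% | 15.0%, 18.2%, 21.6% | 13.6%, 16.9%, 20.5% |
| 100% | 22% | 30.8% | 30.3% |

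The last row does not depend on q.

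**Step 5, what a matched reference would require.** At 80% positive the references are 17.6%, 18.6% and 19.6%. With N = 25 each needs 8 responders for a one-sided 10% test, and P(X ≥ 8 | 0.35) = 69%, against 83% for 7 responders.

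**The case against.** The strongest reply is that 15% is adequate on the documents' own figures. At 40% positive, with 0% to 10% in negatives, the pembrolizumab-alone ORR is 8.8% to 14.8%, always below 15%. The only PD-L1-unselected gastric anti-PD-1 data in the protocol (4.6.2) are no responses among 7 nivolumab patients, a small sample of another drug that points the same way. This stands, and it rules out three stronger readings that a reader might infer:

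- That 15% is right for only one PD-L1 mix. The null is one-sided (ORR at or below 15%), so every PD-L1-poorer mix is also covered.
- That the 10% level is lost as soon as the share passes 40%. At n=25 and 60% positive, the rejection rate is 7.4% with q = 5% and 3.9% with q = 0%. The 40% threshold follows only if 15% is assumed to be exactly right at 40%, which back-solves q as (0.15 − 0.4 × 0.22)/0.6 = 10.3% and leaves no margin by construction. Nothing in the documents says the 15% was derived that way.
- That calling 15% conservative is wrong. A lower null is easier to reject, but against a 40% mix 15% is at or above the implied rate for q up to about 10%. The documents do not show that the word must go.

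A second reply is that mismatch with a historical rate is inherent in a single-arm Phase 1b screen, and that the protocol acknowledges the lack of PD-L1 selection. That argues against replacing the decision rule. It does not explain why a known PD-L1 mix should be ignored when the result is read, or why the planned ORR by PD-L1 was dropped.

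**Conclusion.** The concern holds as a limit on interpretation; the sample size is not in error. The stated power is correct for its inputs. The 15% null protects the 10% level up to a PD-L1-positive share of about 72% down to 48% (n=21) or 74% down to 53% (n=25), as the assumed ORR in negatives goes from 0% to 10%. At 80% positive the level is exceeded across that whole range, and at 100% the no-effect rejection rate is about three times nominal.

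This rests on 22% in positives, which comes from 39 subjects (95% CI 10 to 39, central review) under a different assay definition, and on an assumed q. The enrolled share is not in the documents, so whether the level is actually exceeded is unknown. The SAP analyses ORR in the Tumor Response Evaluable Population, so the final n may be below 25.

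**What to change.** Keep the test against 15% as the primary decision rule. In SAP 4.7.2 add:

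- A supportive, non-gating exact one-sided comparison of gastric confirmed ORR with a PD-L1-matched reference: 22% × observed share with CPS ≥ 1, plus q × observed share with CPS = 0. Show it for q = 0%, 5% and 10%, in subjects of the ORR analysis population with known CPS, and report how many lack CPS.
- A statement that if 15% is rejected but the matched reference is not, the result cannot be attributed to PEGPH20 over PD-L1 mix. If the three values of q disagree, say so; none of them governs.
- A note that the prototype-assay and CPS definitions of positivity differ.

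Restore the descriptive ORR by PD-L1 status from protocol 11.1.7.3, amending SAP 4.7.4 and 4.8, or list its removal in SAP section 5.

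The cost is a little more analysis on data already collected, and a more cautious reading if the cohort is PD-L1-rich. At 80% positive the supportive comparison needs 8 of 25 rather than 7, with power at 35% of about 69% rather than 83%. That loss is the reason to keep it non-gating.
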